8.2.7 Hospitalization

Hospitalization status will be assessed for all participants as outlined in the SoA (Section 1.3.1). Hospitalization is defined as \geq 24 hours of acute care in a hospital or similar acute care facility, including emergency rooms or facilities created to address hospitalization needs during the COVID-19 pandemic. The date and time of hospital admission, date and time of discharge, and primary reason for hospitalization (including if the admission is related to COVID-19) will be recorded. The Sponsor must be notified within 24 hours of site's awareness of a participant's hospitalization.

Participants who report worsening illness from any cause during the study may be referred to their health care provider or a medical facility. Such instances will be recorded at the time of the notification, and during follow-up to assess study endpoints, ie, hospitalization or death.

For any participants who become hospitalized during the study, all study procedures outlined in the SoA (Section 1.3.1), including study intervention administration (if applicable), should be continued if possible. If the hospitalized participant has not completed study intervention and is unable to swallow the capsules or is intubated during hospitalization, then study intervention should be discontinued (Section 7.1).

It is recognized that use of nonstudy personnel may be necessary for some procedures in the study. In such cases, documentation of these responsibilities and source documentation of study intervention administration must be maintained in the site's source documentation as appropriate. If in-person visits are not permitted by the institution in which the participant is hospitalized, a virtual visit (eg, telehealth, telephone) may be performed to collect data per the SoA (Section 1.3.1) that does not require in-person collection. Every attempt should be made to obtain equivalent data from hospital records.

In addition to information regarding hospitalization details, available pertinent information will be collected, including assessment of participant self-reported COVID-19 symptoms (eg, based on Symptom Diary via self-recording or Sponsor-provided interview script, if completed), local COVID-19 testing results, vital signs, supplemental oxygenation use, ventilation procedures, concomitant medications and AEs, including death.

In addition, every effort should also be made for a visit to be scheduled after discharge from the hospital, provided that the visit is within 28 days of initiation of dosing.

8.2.8 Survival Status

Survival status (ie, whether the participant is alive or deceased) will be assessed for participants per the SoA (Section 1.3.1).

Site personnel should attempt to obtain information regarding vital status (including date last known to be alive, hospitalization, date of death, primary cause of death, and COVID-19 contribution to death) from the participant or other sources (eg, family members, other designated secondary contacts, hospital the participant stated they would most likely go to, clinic/hospital/medical records, and local or national databases).

Information about death should be entered in the eCRF within 24 hours of a site becoming aware of a death.

8.2.9 Health Care Utilization for COVID-19

Medically attended COVID-19 (as defined in Section 4.1) will be collected for participants with laboratory-confirmed COVID-19 per the SoA (Section 1.3.1) and entered on the appropriate eCRF. The investigator or qualified designee will assess participant reports to determine if COVID-19 required medical care per the protocol definition of medically attended COVID-19.

8.2.10 Assessment for Severity of COVID-19

The severity of COVID-19 will be assessed for participants who develop laboratoryconfirmed COVID-19 at study visits specified in the SoA and the COVID-19 Confirmation Visit (Section 1.3.1). COVID-19 severity assessments will be performed using the NIAID ordinal scale criteria for COVID-19 severity [Beigel, J. H., et al 2020], as follows:

- 1. Not hospitalized and no limitations of activities
- 2. Not hospitalized with limitation of activities, home oxygen requirement, or both
- 3. Hospitalized, not requiring supplemental oxygen and no longer requiring ongoing medical care (used if hospitalization was extended for infection control or other nonmedical reasons)
- 4. Hospitalized, not requiring supplemental oxygen, but requiring ongoing medical care (related to COVID-19 or to other medical conditions)
- 5. Hospitalized, requiring any supplemental oxygen
- 6. Hospitalized, requiring noninvasive ventilation or use of high-flow oxygen devices
- 7. Hospitalized, receiving invasive mechanical ventilation or extracorporeal membrane oxygenation (ECMO)
- 8. Death

The participant's worst severity experienced since the prior visit should be entered on the appropriate eCRF.

8.2.11 EuroQoL EQ-5D-5L Questionnaire

A quality-of-life assessment will be conducted using the paper EuroQoL EQ-5D-5L questionnaire (as described in Section 4.2.1.5) for participants at study visits specified in the SoA (Section 1.3.1). The questionnaire should be self-administered by participants. If a participant is unable to record responses on the questionnaire on their own, the Sponsor-provided EQ-5D-5L Interviewer Administered Script should be implemented by study staff. If a validated Interviewer Administered Script is unavailable in a language understood by a participant who is unable to record responses on the questionnaire on their own, the quality-of-life assessment does not need to be performed. The EuroQoL EQ-5D-5L questionnaire assessments should be entered on the appropriate eCRF.

8.3 Safety Assessments

Details regarding specific safety procedures/assessments to be performed in this study are provided in the subsections that follow.

Planned time points for all safety assessments are provided in the SoA. The volume of blood to be drawn for clinical laboratory assessments over the course of the study is provided in Appendix 2, Table 12.

8.3.1 Physical Examinations

A directed physical examination will be conducted at the screening visit by a nurse or other qualified health care provider. Height and weight will also be collected and recorded. A nurse or other qualified health care provider will also conduct directed physical examinations targeted at the participant's symptoms/complaints at visits indicated in the SoA (Section 1.3.1). Details of the physical examinations will be provided to the investigator or medically qualified designee (consistent with local requirements) for review and assessment per institutional standard.

8.3.2 Vital Signs

Body temperature, heart rate, respiratory rate, and blood pressure will be assessed. Vital sign measurements should be preceded by at least 5 minutes of rest for the participant in a quiet setting without distractions.

8.3.3 Clinical Safety Laboratory Assessments

Refer to Appendix 2 for the list of clinical laboratory tests to be performed and to the SoA for the timing and frequency.

• The investigator or medically qualified designee (consistent with local requirements) must review the laboratory report, document this review, and record any clinically relevant changes occurring during the study in the AE section of the CRF. The laboratory

reports must be filed with the source documents. Clinically significant abnormal laboratory findings are those which are not associated with the underlying disease, unless judged by the investigator to be more severe than expected for the participant's condition.

- All protocol-required laboratory assessments, as defined in Appendix 2, must be conducted in accordance with the laboratory manual and the SoA.
- If laboratory values from nonprotocol-specified laboratory assessments performed at the institution's local laboratory require a change in study participant management or are considered clinically significant by the investigator (eg, SAE or AE), then the results must be recorded in the appropriate CRF (eg, SLAB).
- For any laboratory tests with values considered clinically significantly abnormal during participation in the study or within 14 days after the last dose of study intervention, every attempt should be made to perform repeat assessments until the values return to normal or baseline or if a new baseline is established as determined by the investigator.

8.3.4 **Pregnancy Testing**

Pregnancy testing requirements for study inclusion are described in Section 5.1. Pregnancy testing should be conducted at screening (may use either serum or urine test; if using a urine test, the test should be sensitive enough to measure 25 mIU/mL hCG) and on Day 14 (serum), approximately 9 days after the last dose of study intervention.

Additional serum or urine pregnancy tests may be performed, as determined necessary by the investigator, or required by local regulation, to establish the absence of pregnancy at any time during the participant's participation in the study.

8.3.5 Pregnancy Follow-up

Pregnancy status (eg, estimated date of conception and delivery date) for female participants of childbearing potential and, female partners of male participants will be collected at the Day 29 (LFU) visit (Section 1.3.1). Collection of pregnancy data for female partners of male participants is not required if the male participant is confirmed to be azoospermic (vasectomized or secondary to medical cause) as documented in medical history.

8.4 Adverse Events, Serious Adverse Events, and Other Reportable Safety Events

The definitions of an AE or SAE, as well as the method of recording, evaluating, and assessing causality of AE and SAE and the procedures for completing and transmitting AE, SAE, and other reportable safety event reports can be found in Appendix 3.

Adverse events, SAEs, and other reportable safety events will be reported by the participant (or, when appropriate, by a caregiver, surrogate, or the participant's legally authorized representative).

The investigator and any designees are responsible for detecting, documenting, and reporting events that meet the definition of an AE or SAE as well as other reportable safety events.

Investigators remain responsible for following up AEs, SAEs, and other reportable safety events for outcome according to Section 8.4.3.

The investigator, who is a qualified physician, will assess events that meet the definition of an AE or SAE as well as other reportable safety events with respect to seriousness, intensity/toxicity and causality.

8.4.1 Time Period and Frequency for Collecting AE, SAE, and Other Reportable Safety Event Information

For participating household contacts, all AEs, SAEs, and other reportable safety events that occur after the participant provides documented informed consent, but before intervention randomization, must be reported by the investigator if the event causes the participant to be excluded from the study, or is the result of a protocol-specified intervention.

From the time of intervention randomization, through 14 days after cessation of study intervention, all AEs, SAEs, and other reportable safety events must be reported by the investigator.

Additionally, any SAE brought to the attention of an investigator at any time outside the period specified in the previous paragraph must be reported immediately to the Sponsor if the event is considered related to study intervention.

For participating index cases, all AEs, SAEs, and other reportable safety events that occur after the participant provides documented informed consent, but before allocation, must be reported by the investigator if the event causes the participant to be excluded from the study, or is the result of a protocol-specified intervention.

Investigators are not obligated to actively seek AEs or SAEs or other reportable safety events in former study participants. However, if the investigator learns of any SAE, including a death, at any time after a participant (index or household contact) has been discharged from the study, and the investigator considers the event to be reasonably related to the study intervention or study participation, the investigator must promptly notify the Sponsor.

All initial and follow-up AEs, SAEs, and other reportable safety events will be recorded and reported to the Sponsor or designee within the time frames as indicated in Table 3.

Exception: A positive pregnancy test at the time of initial screening is not a reportable event unless the participant has received study intervention.

80

Type of Event NSAE	Reporting Time Period: Consent to Randomization/ Allocation Report if: - due to protocol-	Reporting TimePeriod:Randomization/AllocationthroughProtocol-specified Follow-up PeriodReport all	Reporting Time Period: After the Protocol- specified Follow-up Period Not required	Time Frame to Report Event and Follow-up Information to Sponsor: Per data entry guidelines
	specified intervention - causes exclusion			
SAE	Report if: - due to protocol- specified intervention - causes exclusion	Report all	Report if: - drug/vaccine related. (Follow ongoing to outcome)	Within 24 hours of learning of event
Pregnancy/ Lactation Exposure	A positive pregnancy test at the time of initial screening is not a reportable event.	Report all	Previously reported – Follow to completion/ termination; report outcome	Within 24 hours of learning of event
ECI (require regulatory reporting)	Report if: - due to intervention - causes exclusion	Report - Potential DILI - Require regulatory reporting	Not required	Within 24 hours of learning of event
ECI (do not require regulatory reporting)	Report if: - due to intervention - causes exclusion	Report - non-DILI ECIs and those not requiring regulatory reporting	Not required	Within 5 calendar days of learning of event
Cancer	Report if: - due to intervention - causes exclusion	Report all	Not required	Within 5 calendar days of learning of event (unless serious)
Overdose	Not applicable	Report all	Not required	Within 5 calendar days of learning of event

Table 3Reporting Time Periods and Time Frames for Adverse Events and OtherReportable Safety Events

DILI=drug-induced liver injury; ECI=event of clinical interest; NSAE=nonserious adverse event; SAE=serious adverse event.

81

8.4.2 Method of Detecting AEs, SAEs, and Other Reportable Safety Events

Care will be taken not to introduce bias when detecting AEs and/or SAEs and other reportable safety events. Open-ended and nonleading verbal questioning of the participant is the preferred method to inquire about AE occurrence.

8.4.3 Follow-up of AE, SAE, and Other Reportable Safety Event Information

After the initial AE/SAE report, the investigator is required to proactively follow each participant at subsequent visits/contacts. All AEs, SAEs, and other reportable safety events, including pregnancy and exposure during breastfeeding, ECIs, cancer, and overdose will be followed until resolution, stabilization, until the event is otherwise explained, or the participant is lost to follow-up (as defined in Section 7.3). In addition, the investigator will make every attempt to follow all nonserious AEs that occur in randomized participants for outcome. Further information on follow-up procedures is given in Appendix 3.

8.4.4 Regulatory Reporting Requirements for SAE

Prompt notification (within 24 hours) by the investigator to the Sponsor of SAE is essential so that legal obligations and ethical responsibilities towards the safety of participants and the safety of a study intervention under clinical investigation are met.

The Sponsor has a legal responsibility to notify both the local regulatory authority and other regulatory agencies about the safety of a study intervention under clinical investigation. The Sponsor will comply with country-specific regulatory requirements and global laws and regulations relating to safety reporting to regulatory authorities, IRB/IECs, and investigators.

Investigator safety reports must be prepared for SUSARs according to local regulatory requirements and Sponsor policy and forwarded to investigators as necessary.

An investigator who receives an investigator safety report describing an SAE or other specific safety information (eg, summary or listing of SAE) from the Sponsor will file it along with the IB and will notify the IRB/IEC, if appropriate according to local requirements.

8.4.5 Pregnancy and Exposure During Breastfeeding

Although pregnancy and infant exposure during breastfeeding are not considered AEs, any pregnancy or infant exposure during breastfeeding in a participant (spontaneously reported to the investigator or their designee), including the pregnancy of a male participant's female partner, that occurs during the study are reportable to the Sponsor as described in Section 8.4.1.

All reported pregnancies must be followed to the completion/termination of the pregnancy.

Any pregnancy complication will be reported as an AE or SAE.

The medical reason (example: maternal health or fetal disease) for an elective termination of a pregnancy will be reported as an AE or SAE. Prenatal testing showing fetus will be born with severe abnormalities/congenital anomalies that lead to an elective termination of a pregnancy will be reported as an SAE for the fetus.

Pregnancy outcomes of ectopic pregnancy, spontaneous abortion, missed abortion, benign hydatidiform mole, blighted ovum, fetal death, intrauterine death, miscarriage, and stillbirth must be reported as serious events (important medical events). If the pregnancy continues to term, the outcome (health of infant) must also be reported.

8.4.6 Disease-related Events and/or Disease-related Outcomes Not Qualifying as AEs or SAEs

Certain efficacy endpoints including hospitalizations and mortality must be collected throughout the study (ie, during both treatment and follow-up periods). From the time of randomization through 14 days after cessation of study intervention, these events must be reported as described in Section 8.4.1. New hospitalizations and/or deaths that occur after 14 days after cessation of treatment must continue to be assessed for seriousness and causality. However, they must only be reported to the Sponsor within 24 hours as new SAEs if there is evidence to suggest a causal relationship between the study intervention and the SAE.

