- MK-4482-001 Part 1: A total of 218 hospitalized participants with COVID-19 received at • least 1 dose of MOV (72 participants received MOV 800 mg) and 75 participants received placebo. The overall safety profiles observed in P001 were generally comparable for MOV doses and placebo. No trends in AEs or changes in clinical laboratory values were observed as a function of dose or study intervention. The most frequently reported AEs (≥5%) in any MOV group were COVID-19, AST/ALT elevations, constipation, bacterial pneumonia, hyperglycemia, and respiratory failure. The most frequently reported AEs (\geq 5%) in the placebo group were constipation, COVID-19, COVID-19 pneumonia, ALT increased, and respiratory failure. SAEs were reported for 15.4% participants (15.1% participants in the MOV groups combined and 16.0% in the placebo group). One drug-related (as per investigator) SAE (Grade 3 urticaria) was reported for 1 participant (MOV 200 mg). A total of 16 participants had AEs leading to death (6.4% in the MOV groups combined and 2.7% in the placebo group). Most deaths occurred in participants who had severe COVID-19 at baseline (12 of 16), were >60 years of age (13 of 16), had underlying comorbidities (14 of 16), and/or had duration of COVID-19 symptoms >5 days before randomization (12 of 16). None of the deaths were considered drug-related per investigator assessment. The study was stopped due to lack

of clinical benefit in this population (participants already hospitalized prior to randomization) and did not proceed to Part 2.

- MK-4482-002 Part 1: A total of 225 nonhospitalized participants with COVID-19 received at least 1 dose of MOV (74 received at least 1 dose of MOV 800 mg) and 74 participants received placebo in the APaT population. The safety profiles for MOV (all doses) and placebo were comparable. No trends in AEs or changes in clinical laboratory values were observed as a function of dose or study intervention. The most frequently reported AEs (≥5%) were COVID-19 pneumonia in any MOV group and diarrhea and COVID-19 in the placebo group. The percentage of participants with drug-related AEs per the investigator was comparable across all intervention groups. SAEs were reported for 3.6% participants in the MOV combined group and for 5.4% participants in the placebo group. No SAEs were considered drug-related per investigator. Efficacy data are summarized in Section 4.3.1.

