8.1.11 Discontinuation and Withdrawal

Participants who discontinue study intervention before completion of the treatment period should be encouraged to continue to be followed for all remaining study visits after EOT as outlined in the SoA (Section 1.3.1) and Section 8.11.3.

Participants who withdraw from the study should be encouraged to complete all applicable activities scheduled for the Day 29 visit (or the EOT visit if withdrawing prior to completion of the treatment period or the Day 14 visit if withdrawing after the EOT visit and prior to the Day 14 visit; see Section 8.11.3) at the time of withdrawal. Any AEs that are present at the time of withdrawal should be followed in accordance with the safety requirements outlined in Section 8.4.

Hospitalization and survival status at Day 29 are required for all randomized participants and should still be reported for participants who withdraw from the study where permitted by local guidelines.

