9.4.1 Efficacy Endpoints

The primary efficacy endpoint is the percentage of participants with undetectable SARS-CoV-2 in baseline NP swabs developing COVID-19 (laboratory-confirmed SARS-CoV-2 infection with symptoms) through Day 14.

The secondary efficacy endpoints are:

- Percentage of participants (regardless of SARS-CoV-2 results in baseline NP swabs) developing COVID-19 through Day 14
- Percentage of participants with undetectable SARS-CoV-2 in baseline NP swabs developing COVID-19 through Day 29
- Percentage of participants with undetectable SARS-CoV-2 in baseline NP swabs having viral transmission through Day 14

• Percentage of participants with detectable SARS-CoV-2 in baseline NP swabs developing COVID-19 through Day 14

The exploratory efficacy endpoints are:

- Percentage of participants (regardless of SARS-CoV-2 results in baseline NP swabs) developing COVID-19 through Day 29
- Percentage of participants with detectable SARS-CoV-2 in baseline NP swabs developing COVID-19 through Day 29
- Percentage of participants with undetectable SARS-CoV-2 in baseline NP swabs having viral transmission through Day 29
- Percentage of baseline seronegative participants with undetectable SARS-CoV-2 in baseline NP swabs developing anti-SARS-CoV-2 antibodies through Day 29
- Severity of laboratory-confirmed COVID-19 through Day 29 using NIAID ordinal scale criteria
- Participant-reported symptoms severity (for specified COVID-19 symptoms) in participants who develop laboratory-confirmed COVID-19 on or before Day 14
- Change from baseline in SARS-CoV-2 RNA titer and percentage of participants with undetectable SARS-CoV-2 RNA in NP swabs at Day 14 in participants with detectable SARS-CoV-2 in NP swabs at baseline
- Viral RNA mutation rate and detection of treatment-emergent sequence variants as assessed by comparison of viral gene sequencing at baseline and postbaseline in participants who develop laboratory-confirmed COVID-19 on or before Day 14
- Percentage of participants who develop laboratory-confirmed COVID-19 on or before Day 14 utilizing health care related to COVID-19 through Day 29
- Generic health-related quality-of-life in participants through Day 29 via EuroQoL Five Dimension Questionnaire (EQ-5D-5L)

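### Hospitalization and death are called endpoints and collected on everyone to Day 29, but no all-cause comparison between arms covers the last 8 to 10 days

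*Combined protocol and SAP*

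**What the plan says.** Two sections treat these outcomes as endpoints. Section 8.4.6 opens with "Certain efficacy endpoints including hospitalizations and mortality must be collected throughout the study". Section 8.2.7 says that worsening illness is recorded "during follow-up to assess study endpoints, ie, hospitalization or death".

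The data are collected on everyone. Section 8.1.11 states "Hospitalization and survival status at Day 29 are required for all randomized participants", and for participants who withdraw it asks for the same where local guidelines permit. The Schedule of Activities collects hospitalization status at Days 5, 14, 21 and 29 and survival at Day 29.

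On reporting, Section 8.4.6 gives three rules:

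- Early events: "From the time of randomization through 14 days after cessation of study intervention, these events must be reported as described in Section 8.4.1".
- Later events, assessment: "New hospitalizations and/or deaths that occur after 14 days after cessation of treatment must continue to be assessed for seriousness and causality".
- Later events, reporting: "they must only be reported to the Sponsor within 24 hours as new SAEs if there is evidence to suggest a causal relationship".

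Section 8.4.1 sets the same 14-day limit for every AE and SAE, with later SAEs reported only if considered related.

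On analysis, Section 9.4.1 lists no hospitalization or mortality endpoint at any level. The nearest items are both exploratory. One is "Severity of laboratory-confirmed COVID-19 through Day 29 using NIAID ordinal scale criteria". The other is COVID-19-related health care use in participants who develop laboratory-confirmed COVID-19 by Day 14. Table 6 has a Tier 2 row for any serious AE and no row for death or for hospitalization.

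**The concern.** Safety and tolerability is a primary objective. All-cause death and all-cause hospitalization are the two safety outcomes that need no judgment about cause, and the trial collects both on every participant to the end of follow-up. A reader told that they are endpoints would expect to find them compared between arms to Day 29. The plan names no such comparison. After the SAE window closes, whether a death or admission enters the safety comparison depends on the investigator's view of causality.

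The programme's own results give a reason to want a prespecified mortality count. Section 2.2.3.1 reports for hospitalized patients: "A total of 16 participants had AEs leading to death (6.4% in the MOV groups combined and 2.7% in the placebo group". For outpatients it reports AEs leading to death in 2 of 710 on MOV (0.3%) and 12 of 701 on placebo (1.7%). The two point in opposite directions, and neither population is the one studied here.

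**Working it through.** **Step 1. When the SAE window closes.** Section 4.2 places the Day 14 visit 9 days after the last dose. With a scheduled last dose on Day 5, 14 − 5 = 9, which reproduces that figure. Section 8.1.9.1 allows the last dose to fall as late as the evening of Day 6 or the morning of Day 7. Section 8.4.1 closes routine reporting 14 days after cessation.

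Window end = last-dose day + 14. Days outside the window = 29 − window end.

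| Last dose | Window ends | Days outside, to Day 29 | Share of 29 days |
|---|---|---|---|
| Day 5 | Day 19 | 10 | 34% |
| Day 6 | Day 20 | 9 | 31% |
| Day 7 | Day 21 | 8 | 28% |
| Day 1 (assumed extreme: stops at once) | Day 15 | 14 | 48% |

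The first three rows are planned schedules. The last only shows that the window shortens when dosing stops early.

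**Step 2. Where an event is compared between arms.**

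| Event | Named comparison |
|---|---|
| Any death or inpatient admission inside the window, any cause | Any Serious AE, Tier 2, difference with 95% CI |
| After the window, judged drug-related | Same row |
| After the window, participant with laboratory-confirmed COVID-19 | Exploratory NIAID severity through Day 29 (death is category 8); health care use if COVID-19-related and COVID-19 developed by Day 14 |
| After the window, unrelated admission, no laboratory-confirmed COVID-19 | None |
| After the window, unrelated non-COVID death, virus-undetectable at baseline | Only as an imputed COVID-19 case in the Day 29 secondary endpoint (Table 4, applied through Table 5) |

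For example, a participant without COVID-19 who is admitted with an unrelated stroke on Day 23 is recorded and notified, but enters no named comparison. If that participant dies and was virus-undetectable at baseline, the death counts as a case of COVID-19 and not as a death. For a participant virus-detectable at baseline, Day 29 efficacy is exploratory only, with methods left to the sSAP.

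**Step 3. Whether the two hospitalization definitions agree.** Section 8.2.7 requires at least 24 hours of acute care and includes emergency rooms. The SAE definition in Section 10.3.2 counts any inpatient admission, whatever its length. A hospitalization row built on Section 8.2.7 would therefore not match SAE counts exactly.

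**The case against.** The sponsor has a good answer to several stronger readings.

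- **That late events leave SAE reporting because Section 8.4.6 calls them efficacy endpoints.** The documents do not support this. The cutoff is the general rule of Section 8.4.1 and Table 3 for all SAEs. Section 8.4.6 repeats it and adds that late events must still be assessed. Deleting Section 8.4.6 would not move the cutoff. Its heading, and the cross-reference to it in Section 10.3.1 under events that are not AEs, suggest an exemption that its text does not give.
- **That these events are compared nowhere.** This is also too strong. Inside the window every death and inpatient admission enters a Tier 2 comparison, and COVID-19 events reach the exploratory endpoints through Day 29.
- **That the events go unseen.** They do not. Section 8.2.7 requires notice to the Sponsor within 24 hours of the site learning of a hospitalization, and Section 8.2.8 requires eCRF entry of a death within 24 hours. Neither depends on causality.
- **That the 14-day window lacks a rationale.** Section 4.2 states that there is no evidence of delayed toxicity. The longest NHC half-life in Section 2.2.3.1 is about 19 hours, so 14 days is 336 / 19 ≈ 17.7 half-lives. This supports the AE window. It does not explain requiring Day 29 status on everyone and specifying no summary of it.
- **That the earlier mortality figures show harm.** They do not. The hospitalized-patient percentages correspond to about 14/218 versus 2/75, with a two-sided Fisher p of about 0.38. Of the 16 who died, 12 had severe COVID-19 at baseline, and no death was judged drug-related. The figures justify counting deaths and nothing more.

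The sSAP and the separate resource-utilization plans are not available and might contain a summary. But the sSAP is to describe methods for exploratory objectives, and no listed objective concerns all-cause death or hospitalization.

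**Conclusion.** The point holds as a gap in analysis and a contradiction in labels, not as a failure of data collection or notification. For participants whose last dose falls on Day 5 to 7, the final 8 to 10 of 29 days (28 to 34%) have no all-cause comparison of death or hospitalization between arms. The 48% figure applies only to someone who stops on Day 1 and should not be quoted as typical.

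The conclusion rests on two readings. First, the Any Serious AE row counts SAEs as reported under Section 8.4.1, since Section 9.6.2 states no analysis window of its own. Second, the follow-up period named in Table 3 is the 14-day period that Sections 8.4.1 and 8.4.6 both state. If Table 3 meant Day 29, the gap would close, but the text of those two sections would then be wrong.

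The number of affected events is probably small, and the documents give no figure for it. The change is worth making because it gives a primary safety objective a comparison free of causality judgments, from data already in hand.

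**What to change.** Add to Section 9.4.2 and Table 6, in the APaT population, two outcomes by arm: all-cause death through Day 29 and all-cause hospitalization through Day 29. Give each difference with the unstratified Miettinen and Nurminen 95% CI already used for Tier 2, regardless of causality or COVID-19 status. Use the survival and hospitalization status already required for all randomized participants, and show the number in each arm whose Day 29 status is unknown.

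State that the hospitalization row follows the Section 8.2.7 definition, with a footnote that it will not match SAE counts exactly.

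Correct Sections 8.4.6 and 8.2.7 so that they no longer refer to efficacy or study endpoints that Sections 3 and 9.4.1 do not list.

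The cost is two table rows and the wording changes. No new data are needed, and sample size, alpha and power do not change. A descriptive count by arm would be a lesser alternative. The confidence interval is preferable because the plan already gives one for any serious AE.
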